### Secondary Endpoint:

- Other endpoints include mean days of supplemental oxygen, mean days of mechanical ventilation, mean ICU and hospital length of stay, and patient-reported functional status.
- Survival at days 7, 14, 60, 90 days post randomization.

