  - a) Patient must have a blood pressure of <160/96 mmHg prior to receiving study IP
  - b) Patient must have a pulse of <110 beats per minute prior to receiving study IP
    - i. In the event that a patient does not meet blood pressure and/or pulse criteria for IP administration, these vital signs will be rechecked every hour until they have returned to the necessary range.
- c. Glasgow Coma Scale
- d. Respiratory support modality and settings
- e. Blood glucose (for patients with diabetes)
- f. Results of chest x-ray and/or chest CT, if available.
- g. Concomitant medications

10. Day 6 (post-intervention) assessment will include:

- a. Vital signs (heart rate, blood pressure, oxygen saturation, respiratory rate, temperature)
- b. Glasgow Coma Scale
- c. Respiratory support modality and settings
- d. Complete blood count with auto differential\*
- e. Complete metabolic panel\*
- f. Blood glucose (for patients with diabetes)
- g. Inflammatory biomarkers (interleukin-6, c-reactive protein, d-dimer, lactate dehydrogenase)\*
- h. Results of chest x-ray and/or chest CT, if available
- i. Concomitant medications

\*Patients who have been discharged from the hospital prior to Day 6 will be asked to return to the hospital or an outpatient clinic for Day 6 lab work.

11. At ICU discharge (if applicable) and hospital discharge, the following will be gathered:

- a. Intervention or control date and time
- b. Vital signs (heart rate, blood pressure, oxygen saturation, respiratory rate, temperature)
- c. Glasgow Coma Scale
- d. Respiratory support modality and settings
- e. Blood glucose (for patients with diabetes)
- f. Results of chest x-ray and/or chest CT, if available.

12. The following data will be collected following hospital discharge:

- a. Last available results of chest x-ray(s) and/or chest CT(s), if available.
- b. ICU admit and discharge dates and times (if applicable)
- c. Hospital floor admit and discharge dates and times
- d. Dates and times of intubation and extubation (if applicable)
- e. Tracheostomy (if applicable)
- f. ECMO status (and settings, if applicable)
- g. Major adverse cardiac events

- h. Discharge date and time
- i. Discharge location
- j. Concomitant medications
  - a) Including but not limited to current COVID-19 therapies not approved by the FDA, and non-pharmaceutical therapies
- k. Date and time of death (if applicable)

13. Safety assessments will be performed at 30, 60, 90 and 180 days (+/- 7 days) post-discharge

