- a. Safety assessments will include a defined script inquiring about any new or remaining symptoms (e.g., shortness of breath), sleep quality, if the patient feels they are back to baseline and if they have any positive or negative feedback regarding the IP. Open-ended questions regarding any additional concerns the participant may have as well as a specific question regarding any health events or hospitalizations since the last assessment will also be asked.
- b. These assessments will be performed remotely via telephone by study staff. If the assessment is positive (i.e., if the patient reports AEs that are determined to be related to study drug), a clinician will arrange a telemedicine visit to follow up.

14. At 1, 3, 6, and 12 months post-discharge, patients will be emailed a REDCap survey link in order to complete several surveys: PROMIS measures including Dyspnea Severity, Physical Function, Sleep Disturbance, Anxiety, and Depression, as well as the PTSD Checklist (PCL).

- a. If the patient is still hospitalized at any of these time points, respiratory settings and details of physical therapy progress will be gathered from the chart instead.
- b. Window: 1 month +/- 7 days, 3/6/12 months +/- 14 days

15. If a patient is discharged prior to receiving the 5-days of IP administration the patient will still be followed for the duration of the study

Primary Outcome:

1. C-reactive protein levels as assessed prior to and following intervention.

Secondary Outcomes:

1. Death within 30 days
2. ICU-free days at 30 days
3. Hospital length of stay
4. Need for invasive mechanical ventilation
5. Biomarker levels (interleukin-6, d-dimer, lactate dehydrogenase)
6. Need for ECMO
7. Major adverse cardiac events
8. Patient-reported functional status

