## **8. STATISTICAL CONSIDERATIONS**

### **Statistical Methods**

This is a trial with patients randomized to two groups: (1) treatment group with hAF administered intravenously (n=30), (2) control group with intravenous administration of a saline control (n=30). Both groups will receive standard of care in addition to these treatments.

Descriptive statistics, including mean (SD) and median (interquartile range), will be used to assess patient characteristics, and clinical and biomarker outcomes. Comparisons will be made stratified on ICU vs floor status at enrollment for variables. Categorical characteristics will be compared using chi-square test or Fisher exact test. Continuous characteristics will be compared using independent samples t-test or Wilcoxon-Mann-Whitney test. 95% Confidence intervals and *p*-values will be reported from all comparisons. Statistical analyses will be conducted in R and STATA, significance will be assessed at the 0.05 level and all tests will be two-tailed.

Safety will be assessed by descriptive reporting of the incidence proportion of study-related safety adverse events in each study group, with one-sided 95%

binomial exact confidence intervals. No statistical hypothesis test is planned to assess safety, which is consistent even with large Phase III trials. The table below displays the number of patients, out of 30, experiencing no adverse event and the corresponding lower-bound of the 95% exact confidence interval.

Number of Patients with no Related Adverse Events	Number of Patients Experiencing a Related Adverse Event	Lower-bound of the 95% Exact Binomial Confidence Interval for Safety
30	0	90%
29	1	85%
28	2	80%
27	3	76%

If there are 30 patients in the hAF group and if all patients in the hAF group complete the study without experiencing an adverse event we will be able to state with 95% confidence that the safety of hAF is at least 90%.

Exploratory outcomes for safety include, but are not limited to, the following:

- Whether the patient experienced any post-randomization AEs while on study (regardless of relatedness to study participation)
- Whether the patient experienced any post-randomization serious AEs while on study
- Whether the patient experienced any post-randomization unexpected AEs while on study.

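### Survival at days 60 and 90 is left to tests that need a known status for every patient, with no rule for those not reached after discharge

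*Combined protocol and SAP*

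**What the plan says.** Section 3 lists "Survival at days 7, 14, 60, 90 days post randomization" among the secondary endpoints. The synopsis and the outcome list in Section 6 instead give "Death within 30 days", a day that is not in the Section 3 list.

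Section 8 (Statistical Methods) is the whole comparative plan. It says "Categorical characteristics will be compared using chi-square test or Fisher exact test" and "Continuous characteristics will be compared using independent samples t-test or Wilcoxon-Mann-Whitney test". It adds that "significance will be assessed at the 0.05 level and all tests will be two-tailed". It names no time-to-event method, censoring rule, analysis set or rule for missing outcomes.

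Data on death come from two kinds of source:

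- **Hospital stay.** Section 6, item 12, has "Date and time of death (if applicable") collected from the record.
- **After discharge.** Section 6, item 13, schedules safety assessments 30, 60, 90 and 180 days after discharge, each within 7 days either way, and says "These assessments will be performed remotely via telephone by study staff". Item 14 adds emailed surveys at 1, 3, 6 and 12 months after discharge, replaced by chart data for anyone still in hospital.

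Patients discharged early or taken off study drug are still to be followed (Section 6, item 15; Section 7). No record, registry or next-of-kin check of vital status is described.

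**The concern.** A two-by-two test at Day 60 or Day 90 can use only patients whose status on that day is known. Deaths in hospital are likely to be captured, whereas a discharged patient who does not answer may be alive or dead. Unknown status should therefore sit mostly among discharged patients, and the analyst must either drop them or assign them a status. The plan does not choose, and the two choices can err in opposite directions.

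The clocks also differ: the endpoint runs from randomization and the contacts run from discharge. A call made within its window can therefore fall before the day it needs to cover.

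Mortality is a safety-relevant result in this small Phase I/II trial. Its estimates should not rest on a choice made after the data are seen.

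**Working it through.** **The plan's own figures.** The documents give no mortality rate, event count, power or loss rate for survival, so there is no survival figure to reproduce. The only computed figures, the exact one-sided safety bounds for n = 30, do reproduce: 90.5, 85.1, 80.5 and 76.1% against the printed 90, 85, 80 and 76%. The 30 per arm is from Section 8. All death and loss rates below are assumptions.

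**Can status be unknown without dropout?** Suppose a patient leaves hospital 4 days after randomization (assumed; discharge before the five doses are complete is foreseen). At the early edge of the windows, the 60-day call falls on Day 4 + 53 = 57 and the 90-day call on Day 4 + 83 = 87. Each is 3 days short of its endpoint day, and only a later successful contact settles status. Any completed contact about a month after discharge settles days 7 and 14.

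**One arm, 3 deaths in 30, 6 discharged patients unreached:**

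| Handling of the 6 | Mortality |
|---|---|
| Dropped | 3/24 = 12.5% |
| Counted alive (best case) | 3/30 = 10.0% |
| Counted dead (worst case) | 9/30 = 30.0% |

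**Expected values.** Let p be in-hospital mortality, q mortality after discharge, and l the share of discharged patients lost, independently of later death.

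- True mortality = p + (1−p)q.
- Lost patients dropped: [p + (1−p)(1−l)q] / [p + (1−p)(1−l)].
- Lost patients counted alive: p + (1−p)(1−l)q.

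With q = 0 and lost patients dropped:

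| p | l = 10% | l = 20% | l = 30% |
|---|---|---|---|
| 10% | 11.0% | 12.2% | 13.7% |
| 20% | 21.7% | 23.8% | 26.3% |

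With p = 10%, q = 5% and l = 20%, the truth is 0.10 + 0.90 × 0.05 = 14.5%. Dropping gives 0.136/0.82 = 16.6%, and counting alive gives 13.6%. The direction of the error depends on the handling.

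**Arm difference with equal true mortality.** Loss of 0% against 20% gives 10.0% against 12.2% (p = 10%) or 20.0% against 23.8% (p = 20%), a gap of 2 to 4 points. For scale, the half-width of a 95% interval for the difference at 10% in each arm is 1.96 × √(2 × 0.1 × 0.9/30) = 15 points.

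Simulated Fisher rejection rates (30 per arm, 40,000 runs, no true difference; exact enumeration agrees to within 0.2 point):

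| Loss by arm | p = 10% | p = 20% |
|---|---|---|
| 0% and 0% | 0.9% | 2.3% |
| 0% and 20% | 3.3% | 4.6% |
| 5% and 30% | 3.8% | 5.6% |

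**Does Kaplan-Meier alone solve it?** Take the same 3 deaths and 6 losses. If all losses follow the last death, the estimate is 1 − (29/30)(28/29)(27/28) = 10.0%. If all 6 are censored before the first death, it is 1 − (23/24)(22/23)(21/22) = 1 − 21/24 = 12.5%, the same as dropping them. A simulation of 200,000 patients with 20% of discharged patients lost points the same way. When loss is at discharge, Kaplan-Meier gives 11.5% against a true 10%, and 22.8% against a true 20.0%. When loss comes after the 30-day call, there is essentially no bias.

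**The case against.** The case against is substantial, and much of it stands.

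- **Overstated mortality.** A reader might infer that the plan will overstate mortality. The documents do not support that: overstatement requires dropping unreached patients, and no section says they will be dropped. That all in-hospital deaths are known and that the lost are survivors are also inferences. Withdrawal of consent, allowed at any time, is another route to missing status.
- **All four days.** A reader might extend the problem to every listed day. Days 7 and 14 are settled by any later contact.
- **A false treatment effect.** A reader might expect a misleading significant result. That needs unequal loss, for which a double-blind trial gives no evident reason. Even 0% against 20% loss leaves Fisher rejection below 5%; only the extreme case at 20% mortality passes it, at 5.6%.
- **Follow-up is better than calls alone.** A survivor must miss every contact from Day 90 on, including the 180-day call and the 6- and 12-month surveys, to be unknown at Day 90. Adverse events are recorded through Day 180, and a death is a serious event that the site reports once it knows of it. This makes heavy loss less likely, but reporting still depends on someone learning of the death.
- **The test is not the core fault.** Survival at a fixed day is a valid binary endpoint when status is known, and Kaplan-Meier can show the same bias when patients are lost at discharge. Finding out vital status therefore matters more than the choice of test.

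What survives all this is that no source other than contact with the patient is scheduled after discharge, and no rule covers those not reached.

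**Conclusion.** The point holds for days 60 and 90. Section 8 leaves these comparisons to tests that need complete status, while the follow-up can leave status unknown, and the handling of unknowns is open. The likely distortion is a few points per arm: about 1 to 4 at 10% mortality and 2 to 6 at 20%, if 10 to 30% of discharged patients are lost, none of them died, and they are dropped. It runs the other way, by about 1 point, if lost patients are counted alive with 5% post-discharge mortality and 20% loss. A spurious arm gap would be similarly small beside the imprecision of 30 per arm. The harm is to the mortality estimates and their intervals more than to the error rate of the tests.

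Separate tests at days 7, 14, 30, 60 and 90 would also re-use the same early deaths, each at the 0.05 level.

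**What to change.** 1. **Section 6.** Add a medical-record vital-status check at days 60 and 90 after randomization for every patient not confirmed alive by a later contact. Record the last date known alive. This is the main remedy.
2. **Section 8.** Estimate survival from randomization by Kaplan-Meier, censored at the last date known alive. Report each arm at days 7, 14, 30, 60 and 90, and the Day 90 difference with its 95% confidence interval. Use one log-rank test in place of a test at each day. Section 8 says "Comparisons will be made stratified on ICU vs floor status at enrollment for variables"; state whether that covers this test.
3. **Sensitivity analysis.** For any status still unknown, report best and worst cases, including opposite assumptions in the two arms, because Kaplan-Meier is also biased upward if patients are lost at discharge.
4. **Consistency.** Reconcile the days in Section 3 with the 30-day death outcome in the synopsis and Section 6, and state how contacts timed from discharge supply status timed from randomization.

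The cost is a chart check for unreached patients, one extra date field if the last contact date is not already stored, and slightly more analysis. Dates of death are already collected. A record check may miss deaths outside the health system, so step 3 is still needed.

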## 4. BACKGROUND AND HYPOTHESES

Early data in the COVID-19 pandemic suggests that women who have given birth while actively infected may not transmit the virus to the baby, amniotic fluid, or breast milk. Given the use of amniotic products for treatment of inflammation in other situations, described below, our group proposes an experimental and innovative use of hAF as its impact on cardiopulmonary failure has not been previously investigated. We hypothesize that systemic administration of human amniotic fluid (hAF) may assist in decreasing inflammation in patients infected with COVID-19.

Human amniotic membrane and human amniotic fluid have been shown to reduce inflammation, have antimicrobial properties, and low risk of immunogenicity. hAF is devoid of any cellular products (not to be confused with umbilical cord-derived, AF-derived stem cell products, or AF embolism). Purified hAF is a cell-free, non-antigenic solution of >1000 proteins that mother nature developed. Hence, amniotic products make ideal biocompatible scaffolds for the treatment of diverse conditions, including intractable epithelial defects, burns,

Randomized, Double-blinded, Placebo-Controlled Clinical Trial to Determine Safety and Feasibility of using an Acellular Sterile Filtered Amniotic Fluid as a Treatment for COVID-19 Patients.

PI: [name]

Version: 17 JUL 2020

diabetic/peripheral vascular ulcers, partial limbal cell deficiencies, peripheral nerve regeneration, tendon repair, and Stevens-Johnson syndrome. The University of Utah is well-poised to perform this investigation, as human amniotic membrane (hAM) is currently being used here as a clinical tissue allograft in burn patients, for digital ulcers in scleroderma patients, as a nerve wrap to protect nerves from adhesions post-surgery, and as trachea-stenosis-tracheal stent covering. Likewise, there is an ongoing study exploring post-cardiac surgery atrial fibrillation, thought to be associated with local and systemic inflammation, and the impact of using hAM as a substitute pericardial patch to decrease post-operative inflammation. While results are not yet available, the six (of twelve) patients who have randomized to treatment have had no ill effects from the placement of the membrane. With regard to fluid, hAF has been successfully injected into >500 burn patients to augment graft survival at the University of Utah. hAF is also currently being used experimentally under IND approval at the University of Utah to treat ocular graft versus host disease and ocular PRK. An IRB application to study hAF to treat chronic wounds is pending. IND applications have been or are being submitted to the FDA to treat osteoarthritis and radicular lower back pain.

In basic science laboratories here at the University of Utah, we have demonstrated that rats undergoing myocardial ischemia reperfusion have a marked decrease in myocardial injury and fibrosis if they receive either intramyocardial or systemic intravenous injection of hAF. Thus, there is conceptual attractiveness in the potential impact of systemic administration of hAF in COVID-19 patients. Many COVID-19 patients, in addition to succumbing to acute hypoxic respiratory failure, are plagued with cardiac manifestations including myocarditis, accelerated heart failure, and arrhythmias. Lung pathology specimens from the SARS-1 epidemic in 2005 demonstrated diffuse alveolar damage with extensive fibrosis. Likewise, lung pathology in COVID-19 patients undergoing lung resection for lung cancer (i.e., non-autopsy pathology) revealed edema and patchy, inflammatory cellular infiltrates, particular with macrophages. As COVID-19 causes an aggressive inflammatory and fibrotic response, this suggests that hAF, by mitigating inflammation and decreasing fibrosis, could impact the natural history of COVID-19 infected patients.

Importantly, the University of Utah is home to the Cell Therapy and Regenerative Medicine (CellReGen) program. CellReGen is unique in the world for being able to process and manufacture hAF for clinical use. hAF has previously been FDA-approved as a human cellular and tissue product (HCT/P) under 21 CFR 1271 for tissue injury. It has been generated by CellReGen, utilized widely, and safely used in thousands of patients without demonstrable toxicity. If hAF proves effective, we are confident that CellReGen could mobilize mass quantities of hAF in a relatively short period of time, which could be used to treat COVID-19 nationally.

Ten patients were enrolled in a pilot study. These patients were diagnosed with COVID-19 by SARS-CoV-2 positivity by RT-PCR test. Patients were 40% female with an average age of 51.9 years old (range 24-76). Patients were 50% white, with two patients identifying as American Indian/Alaskan Native, three patients identifying as Hispanic (one Hispanic/white), and one as unknown or other.

Based on the findings of the pilot study, we plan to modify the trial and recruit only patients who are considered moderately ill. Patients who are endotracheally intubated on mechanical ventilation will not be eligible.

Summarily, merging the COVID-19-related observations and our experience with hAF, we hypothesize that systemic administration of hAF may assist in the treatment of this disease in moderately ill patients, specifically by reducing inflammation in the lungs. Ideally, this treatment could decrease the number of infected patients requiring critical care, thereby impacting patient outcomes as well as the socioeconomic burden of this pandemic on precious resources.

## 5. ELIGIBILITY CRITERIA

### **Population:**

Hospitalized adult patients with confirmed acute COVID-19 infection.

### **Inclusion:**

1. Age  $\geq 18$
2. SARS-CoV-2 positivity by RT-PCR test, obtained within 14 days of enrollment
3. Hospitalized

Randomized, Double-blinded, Placebo-Controlled Clinical Trial to Determine Safety and Feasibility of using an Acellular Sterile Filtered Amniotic Fluid as a Treatment for COVID-19 Patients.

PI: [name]

Version: 17 JUL 2020

4. COVID-19 symptomatic (cough, fevers, shortness of breath, and/or sputum production)
5. Has a room air pulse oximetry of  $\leq 94\%$  and requires supplemental oxygen therapy
6. Patients of child bearing potential who agree to use acceptable methods of contraception for 90 days after last administration of study IP
7. Patients who are receiving standard of care therapies for COVID-19 that are not FDA approved are eligible for this study
8. Patients must be able to consent to the study (i.e., Glasgow Coma Score of  $\geq 14$ )
9. Patients are required to have controlled blood pressure of  $< 160/96$  and have a pulse of  $< 110$  at the time of study drug administration.

**Exclusion:**

1. Patients on invasive mechanical ventilation (e.g., endotracheal intubation)
2. Chronic home oxygen utilization
3. Clinically significant home use of immunosuppressive medications, including more than 20mg of steroid (e.g., prednisone) per day, monoclonal antibodies, or chemotherapy medications. Patients who are not chronically immune suppressed are eligible for participation. Patients who are prescribed steroids, including dexamethasone, for the purpose of treating COVID-19 prior to the patient's study hospital admission will not be excluded.
4. Women who are pregnant, breastfeeding or become pregnant during the study
5. Patients on non-invasive positive pressure ventilation
6. Patients on  $>12$  liters per minute via non-rebreather (NRB) or  $>80\%$  oxygen via high flow nasal cannula
7. Patients who in the opinion of the Investigator has impending respiratory failure, defined as requiring rapidly escalating oxygen supplementation
8. Patients with a hemoglobin  $< 9$  mg/dL
9. Patients diagnosed with stage 4 or 5 chronic kidney disease (CKD)
10. Patients with diagnosed with NYHA class 3 or 4 congestive heart failure (CHF)
11. Patients with a left ventricular assist device (LVAD)
12. Patients with thromboembolic phenomena
13. Patients with Type 2 and above heart block
14. Patients with established positive bacterial blood cultures prior to enrollment
15. Patients with ongoing pericardial effusion, or ascites
16. Patients with clinically significant arrhythmia
17. Patients with liver function tests (ALT or AST)  $> 3X$  normal
18. Patients with untreated HIV infection
19. Patients diagnosed with end-stage organ disease

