	
Exclusion:
 

1. Patients on invasive mechanical ventilation (e.g., endotracheal intubation)

2. Chronic home oxygen utilization

3. Clinically significant home use of immunosuppressive medications, including more than 20mg of steroid (e.g., prednisone) per day, monoclonal antibodies, or chemotherapy medications. Patients who are not chronically immune suppressed are eligible for participation. Patients who are prescribed steroids, including dexamethasone, for the purpose of treating COVID-19 prior to the patient's study hospital admission will not be excluded.

4. Women who are pregnant, breastfeeding or become pregnant during the study

5. Patients on non-invasive positive pressure ventilation

6. Patients on >12 liters per minute via non-rebreather (NRB) or >80% oxygen via high flow nasal cannula

7. Patients who in the opinion of the Investigator has impending respiratory failure, defined as requiring rapidly escalating oxygen supplementation

8. Patients with a hemoglobin < 9 mg/dL

9. Patients diagnosed with Stage 4 or 5 chronic kidney disease (CKD)

10. Patients with diagnosed with Class 3 or 4 congestive heart failure (CHF)

11. Patients with a left ventricular assist device (LVAD)

12. Patients with current thromboembolic phenomena

13. Patients with Type 2 and above heart block

--	---

Randomized, Double-blinded, Placebo-Controlled Clinical Trial to Determine Safety and Feasibility of using an Acellular Sterile Filtered Amniotic Fluid as a Treatment for COVID-19 Patients.

PI: [name]

Version: 17 JUL 2020

	

14. Patients with established positive bacterial blood cultures prior to enrollment

15. Patients with ongoing pericardial effusion, or ascites

16. Patients with clinically significant arrhythmia

17. Patients with liver function tests (ALT or AST) >3x normal

18. Patients with untreated HIV infection

19. Patients diagnosed with end-stage organ disease

Study Product, Dose, Route, Regimen	
hAF will be delivered to the clinical setting on the date of application. Dose is 10mL/day for 5 days; patients may be discharged prior to completing regimen.
 
Route: Intravenous (IV) Push

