## 6. STUDY DESIGN AND PROCEDURES

1. Patients will be screened via the electronic medical system, and/or noted and communicated to the study team by physicians in the units.
2. Patient will be called for e-consent.
3. Patients of childbearing potential will receive a pregnancy test
4. Enrolled patients will be randomized to intervention or control with random permuted blocks of 2-4 via sealed envelope or secured electronic randomization tool that will be selected after consent. Patients or treating clinicians will not be notified of treatment assignment.
5. Amniotic fluid will be procured by the Cell Therapy and Regenerative Medicine group here at the University of Utah. Product will be delivered, either frozen or thawed, by this group to the relevant hospital unit/floor.
6. After consent, but prior to initial intervention, the following measurements will be collected:
  - a. Demographics (age, sex, height, weight, race/ethnicity, study hospital admit date and time)
  - b. Medical history
  - c. Concomitant medications
  - d. Confirmation of negative pregnancy test, if applicable
  - e. Date of symptom onset
  - f. Date of confirmed SARS-CoV-2 positivity by RT-PCR
  - g. Vital signs (heart rate, blood pressure, oxygen saturation, respiratory rate, temperature)
    - a) Patients must have a blood pressure of <160/96 mmHg prior to receiving study IP
    - b) Patients must have a pulse of <110 beats per minute prior to receiving study IP
  - h. Glasgow Coma Scale
    - a) Patient must have a GCS score of  $\geq 14$  prior to consent
  - i. Respiratory support modality and settings
  - j. Complete blood count with auto differential
  - k. Complete metabolic panel
  - l. Blood glucose (for patients with diabetes)
  - m. Inflammatory biomarkers (interleukin-6, c-reactive protein, d-dimer, lactate dehydrogenase)
  - n. Results of chest x-ray and/or chest CT, if available.
7. Patients will receive either 10ml IV hAF or 10ml normal saline (control) each day for 5 consecutive days. hAF and saline with similar lot numbers will be prepared in order to maintain blinding between both clinicians and patients.
8. For 3 hours following IP administration, patients will be placed on continuous monitoring (e.g., pulse oximetry, blood pressure) and monitored for infusion reactions.
9. Assessments on Days 1-5 will include:
  - a. Intervention or control date and time

- b. Vital signs (heart rate, blood pressure, oxygen saturation, respiratory rate, temperature)

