## Protocol Deviations

A **protocol deviation** is nonadherence to protocol-specific study procedures or schedules that does not involve inclusion/exclusion criteria, primary objective variable criteria, and/or GCP guidelines. Deviations are considered minor and do not impact the study.

A **protocol violation** is any significant divergence from the protocol, i.e., nonadherence on the part of the patient, the investigator, or the Sponsor to protocol-specific inclusion/exclusion criteria, primary objective variable criteria, and/or GCP guidelines. Protocol violations will be identified and recorded by the study site personnel on the CRF.

Deviations and violations will be reported to the Principal Investigator and the Sponsor and, if necessary (i.e., if the deviation or violation results in an adverse or serious adverse event, the DSMB.

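### Exclusion 8 gives the hemoglobin cut-off in mg/dL in both eligibility lists, so read literally it excludes no one; exclusion 12 (thromboembolism) is worded differently in the two lists

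*Combined protocol and SAP*

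**What the plan says.** The protocol carries two exclusion lists, one in Section 1 (Synopsis) and one in Section 5 (Eligibility Criteria). Each has 19 items in the same order. Exclusion 8 opens with "Patients with a hemoglobin" in both.

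- **Exclusion 8, Synopsis:** "Patients with a hemoglobin < 9 mg/dL".
- **Exclusion 8, Section 5:** "Patients with a hemoglobin $< 9$ mg/dL". The number and the unit are the same.
- **Exclusion 12, Synopsis:** "Patients with current thromboembolic phenomena".
- **Exclusion 12, Section 5:** "Patients with thromboembolic phenomena".

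The only other place where a hemoglobin value would arise is the blood count. Section 6 lists it at baseline as "Complete blood count with auto differential", and again on Day 6, with no unit. Hemoglobin itself is named nowhere else in the available text, and nothing says which list governs if the two differ.

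Section 7 (Protocol Deviations) places eligibility on the more serious side of its classification. A protocol violation is a significant divergence from the protocol, and the definition includes "nonadherence on the part of the patient, the investigator, or the Sponsor to protocol-specific inclusion/exclusion criteria". Violations are to be recorded on the case report form.

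**The concern.** An eligibility cut-off is a decision rule: staff compare a laboratory value with the printed number and accept or decline the candidate. Exclusion 8 cannot work that way as printed, because the unit puts the cut-off far below any value a laboratory would report for a living adult. The two lists agree with each other, so comparing them does not expose the slip, and no other section corrects it.

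Two things are at stake. A site that applies the text as approved has no working hemoglobin exclusion and could enrol patients whom the criterion was probably meant to keep out. A site that reads another unit into the text is relying on a threshold the protocol does not state, and different sites could do so differently. The sample size section allows expansion to other hospitals if cases run short, which would add readers of the same text.

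Exclusion 12 raises a different problem. The lists should be identical, but one has a time qualifier that the other lacks. A candidate whose thromboembolic event has resolved might be accepted on one reading and declined on another.

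**Working it through.** No sample size, power or event calculation is involved, and the plan derives no figure that could be reproduced. The check is a unit conversion and a comparison of the two lists.

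**Exclusion 8**

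Inputs:
- Printed cut-off: 9 mg/dL (Synopsis and Section 5).
- Conversion: 1 g = 1,000 mg.
- Adult inpatient hemoglobin: 3 to 20 g/dL. This is an assumption, deliberately wide; the documents give no range.

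Steps:
1. Cut-off in g/dL: 9 / 1,000 = 0.009 g/dL.
2. Assumed range in the printed unit: 3 × 1,000 = 3,000 mg/dL, and 20 × 1,000 = 20,000 mg/dL.
3. Distance from the cut-off: 3,000 / 9 ≈ 333 at the low end, and 20,000 / 9 ≈ 2,222 at the high end.
4. A candidate is excluded only if the value is below 9 mg/dL. Every value in the assumed range is at least about 333 times higher, so the literal criterion excludes no one. The exact limits of the range do not matter, because any clinically conceivable low value gives the same answer.

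If the sponsor meant g/dL with the same number, the printed threshold is too low by a factor of 1,000. That intention is plausible but is not stated.

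The unit appears once in a table and once in a numbered list and is the same both times, so a fault in text conversion is an unlikely explanation.

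**Exclusion 12**

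Section 5 can be read in two ways, as referring to present events only or to events at any time:

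| Candidate | Synopsis | Section 5, present events only | Section 5, events at any time |
|---|---|---|---|
| Event present at screening | Excluded | Excluded | Excluded |
| Past, resolved event | Not excluded | Not excluded | Excluded |
| No event | Not excluded | Not excluded | Not excluded |

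The readings differ only in the middle row. The wider reading is not fanciful: elsewhere in the same Section 5 list a time word is added where one is wanted. Exclusion 15 limits pericardial effusion and ascites to ongoing cases, and exclusion 14 ties blood cultures to the time before enrollment. A reader could take the absence of such a word in exclusion 12 as deliberate.

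The lists are also not word-for-word copies elsewhere. Exclusion 10 names the NYHA classification in Section 5 but not in the Synopsis. That difference is smaller, but it shows that the two texts were edited separately.

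**The case against.** The strongest case on the other side is that these are editorial slips with little practical effect. Clinical staff see hemoglobin values every day and would recognise the unit as wrong. The number is 9 in both lists, so no rival threshold competes with it. A site that reads g/dL applies a stricter rule than the printed one, so every patient it enrols also satisfies the printed criterion. For exclusion 12, the Section 5 wording is naturally read in the present tense and does not mention a history of events; on that reading the two lists agree.

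Much of this stands, and it rules out several stronger readings that a reader might infer:

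- **That the exclusion is inoperative in practice.** The arithmetic describes the text. The documents contain nothing on how sites apply it, so a figure of zero patients excluded is not an operating fact.
- **That any departure from the printed cut-off is a protocol violation.** Section 7 speaks of significant divergence, and a site that declines candidates under a stricter reading enrols no one the printed text would bar.
- **That a safety exclusion has failed.** The available text gives no purpose for exclusion 8.
- **That the two lists flatly contradict each other for every candidate with a past thromboembolic event.** Section 5 permits the present-tense reading, so this is an ambiguity, and the number of such candidates is not given.

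The objection does not make the text correct. Recognising a slip still leaves staff to supply a threshold that the approved protocol does not state, and the possibility of a literal reading remains.

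**Conclusion.** The point holds in a limited form. Exclusion 8 is wrong as written in both places where it appears. Taken literally it excludes no one, and nothing else in the document repairs it. This rests on the assumed range of 3 to 20 g/dL, but the margin is so large (at least about 333-fold) that the conclusion is not sensitive to it. How often the literal reading would change an enrolment decision cannot be estimated from the documents; it may be rarely or never.

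Exclusion 12 is an ambiguity to be reconciled. It concerns only candidates with a past, resolved event, whose share the documents do not give.

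Neither item touches the endpoints, the sample size of 60 or the planned analyses. The correction should be made because an eligibility list ought to be enforceable as printed and the change is nearly free.

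**What to change.** 1. The sponsor confirms the intended hemoglobin unit and threshold, and exclusion 8 is corrected in both the Synopsis and Section 5. No value is proposed here.
2. The sponsor decides whether exclusion 12 covers current events only or also past ones, and both lists then carry the same wording.
3. In the same pass, the two lists are compared line by line so that smaller differences, such as the one in exclusion 10, are removed.

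The cost is a few words in two lists at the next amendment. Section 12 (Amendments: IRB and FDA) requires IRB review and approval even for administrative changes, so an informal correction at a site is no substitute. There is no effect on sample size, data collection or analysis.
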